## 7.6 TTI-621 Intrasubject Dose Intensification – Additional Assessments Every Week of Dose Intensification (only applicable to Part 3)

For subjects who are dose intensified at Week 3 through Week 8, the following assessments are required on Day 1, only if not already part of the scheduled weekly visit. For the TTI-621 monotherapy cohorts, assessments will be performed at the indicated time relative to infusion of TTI-621. For subjects in the combination cohorts, pre-infusion assessments will be performed relative to the start of the combination partner infusion, as applicable.

- serum for PK at end of infusion and 4 hours after Time 0 (see [Table 7-2](#))
- whole blood for receptor occupancy: pre-infusion and at end of infusion (approximately 60 minutes after Time 0,  $\pm$  15 minutes)
- hematology at 4 hours after Time 0. Additional hematologic monitoring should be instituted at the discretion of the treating Investigator.
- serum chemistries at 4 hours after Time 0

## 7.7 Week 4

On Day 1 of Week 4 (Day 22 of treatment), the below tests and observations will be performed. For the TTI-621 monotherapy cohorts, assessments will be performed at the indicated time relative to the infusion of TTI-621. For subjects in the combination cohorts, assessments will be performed relative to the infusion of the combination partner, as applicable. All of these assessments can be performed up to 24 hours pre-infusion, with the exception of vital signs and PK. For Part 3 only, if intrasubject dose intensification occurs at this visit please also refer to [Section 7.6](#) for additional assessments.

- symptom driven physical examination and ECOG score
- body weight
- vital signs prior to infusion and at completion of infusion (60 minutes after Time 0 [ $\pm$  15 minutes]). For subjects in the combination cohorts, the latter timepoint (60 minutes after Time 0) is to be done only if the combination partner and TTI-621 are administered more than 60 minutes apart; performed per the institutional standard of care. For subjects under Part 4 vitals are not required at end of infusion. Refer to [Appendix D. Table 2](#).
- urine or serum pregnancy test for women of childbearing potential
- Serum for PK:
  - For Part 3: serum for PK trough levels (pre-dose)
  - For Part 4: serum for PK trough levels (pre-dose). If a priming regimen is used see [Appendix F](#) for revised sampling timepoints.
- Hematology:
  - For Part 3: pre-dose (results must be available prior to start of infusion). Further hematologic monitoring should be instituted at the discretion of the treating Investigator.
  - For Part 4: pre-dose (results must be available prior to start of infusion). Further hematologic monitoring should be instituted at the discretion of the treating Investigator. If a priming regimen is used, see [Appendix F](#) for revised sampling timepoints.
- serum chemistries
- serum for ADA
- AEs
- concomitant medications
- coagulation panel only for Part 4
- resting 12-lead ECG within 60 minutes prior to infusion ( $\pm$  30 minutes) only for Part 4
- biomarkers ( $\pm$  15 minutes; see Study Manual for details of sample splitting, preparation, and shipping):
  - For Part 4: If a priming dose is used additional whole blood for receptor occupancy is required. See [Appendix F](#) for additional sampling timepoints.

## 7.8 Week 5-7

On Day 1 of Week 5, the below tests and observations will be performed. For the TTI-621 monotherapy cohorts, assessments will be performed at the indicated time relative to the infusion of TTI-621. For subjects in the combination cohorts, assessments will be performed relative to infusion of the combination partner, as applicable. All assessments can be performed up to 24 hours pre-infusion, with the exception of PK. For Part 3 only, if intrasubject dose intensification occurs at this visit please also refer to [Section 7.6](#) for additional assessments.

- symptom driven physical examination and ECOG score
- vital signs, performed per the institutional standard of care
- body weight
- Part 3 and Part 4: hematology (results must be available prior to study drug). For Part 4, if a priming dose is required see [Appendix F](#).
- Part 3 and Part 4: serum for PK trough levels (pre-dose). For Part 4, if a priming dose is required see [Appendix F](#).
- AEs
- concomitant medications

### 7.8.1 Week 5 (Part 4 only)

The following assessments are also required in addition to the week 5 assessments specified above, for Part 4 only.

- biomarkers ( $\pm$  15 minutes; see Study Manual for details of sample splitting, preparation, and shipping):
  - For Part 4: If a priming dose is used additional whole blood for receptor occupancy is required. See [Appendix F](#) for additional sampling timepoints.

### 7.8.2 Week 6 (Part 4 only)

The following assessments are also required in addition to the week 6 assessments specified above, for Part 4 only.

- Serum for PK – at completion of infusion (approximately 60 minutes after Time 0), 2 hours and 4 hours after Time 0 ( $\pm$  15 minutes), Day 2 (approximately 24 hours after Time 0) and Day 4 (approximately 72 hours after Time 0). See [Table 7-2](#).

- Whole blood for receptor occupancy – pre-dose and at end of infusion (approximately 60 minutes after Time 0)

### 7.8.3 Week 7 (Part 4 only)

The following assessments are also required in addition to the week 7 assessments specified above, for Part 4 only.

- Whole blood for receptor occupancy pre-dose

## 7.9 Week 8

The below tests and observations will be performed on Day 1 of Week 8 unless otherwise stated. For subjects in the monotherapy cohorts, the procedures listed below will be performed at the indicated time relative to TTI-621 infusion. For subjects in the combination cohorts, pre-infusion procedures will be relative to the combination agent infusion, where applicable. Post-infusion procedures will be relative to the TTI-621 infusion. All assessments can be performed up to 24 hours pre-infusion, with the exception of PK and biomarkers.

- symptom driven physical examination and ECOG score
- vital signs, performed per the institutional standard of care
- body weight
- disease assessment at the end of the week (see [Appendix D. Table 3](#))
  - For CTCL and PTCL subjects, central submission of radiographic disease assessments is required. Part 4 will not require submission of scans for central review in real time but retrospective submissions might be requested by sponsor.
  - CTCL subjects only: mSWAT, CAILS (if applicable) and photographs
- Fresh tumor sample from an identified target lesion (CTCL subjects: required if feasible to perform biopsy, all other tumor types: optional).
- Peripheral blood and blood smear for central pathology review (See [Appendix D. Table 3](#)). Refer to the Laboratory Manual for additional details; not required for Part 4
- resting 12-lead ECG
- Post-dose: QOL by FACT-G (all subjects) and SKINDEX29 (CTCL only)
- urine or serum pregnancy test for women of childbearing potential
- serum chemistries

- hematology (results must be available prior to start of infusion). Further hematologic monitoring should be instituted at the discretion of the treating investigator.
- serum for PK (see [Table 7-2](#)):
  - Part 3: trough levels pre-infusion and completion of infusion (approximately 60 minutes after the start of infusion [i.e., Time 0]), 2 hours and 4 hours after Time 0, Day 2 (approximately 24 hours after Time 0), and Day 4 (approximately 72 hours after Time 0)
  - Part 4: trough levels pre-infusion
- biomarkers ( $\pm$  15 minutes; see Study Manual for details of sample preparation and shipping):
  - bone marrow aspirate for receptor occupancy (only for subjects with bone marrow based disease), to align with the response assessments. Not required for Part 4
  - serum for cytokine/chemokine panel pre-infusion, at completion of infusion (approximately 60 minutes after Time 0), 4 hours after Time 0, and Day 2 (approximately 24 hours after Time 0); not required for Part 4.
  - Part 3: whole blood for receptor occupancy pre-infusion and at completion of infusion (approximately 60 minutes after Time 0); not required for Part 4.
  - whole blood for innate and adaptive response assay pre-infusion, not required for Part 4
  - whole blood for TCR V $\beta$  sequencing pre-infusion, not required for Part 4
- urinalysis (Part 3 only)
- coagulation (Part 4 only)
- serum for ADA analysis
- AEs
- concomitant medications

## 7.10 Weeks 9 and Higher

### 7.10.1 Phase 1b Part 3

The following assessments are applicable for Part 3.

For subjects in the monotherapy cohorts, the procedures listed below will be performed at the indicated time relative to the infusion of TTI-621. For subjects in the combination cohorts, pre-infusion procedures will be relative to the combination agent infusion, where applicable. Post-infusion procedures will be relative to the TTI-621 infusion. All assessments can be performed up to 24 hours pre-infusion, with the exception of PK and biomarkers. The below testing intervals represent a minimum; subjects with an ongoing abnormality should be monitored more frequently as clinically indicated.

- symptom driven physical examination and ECOG score Day 1 of Week 12 and every 4 weeks thereafter
- vital signs, performed per the institutional standard of care
- body weight measured every other week (Week 10, 12, etc.). After Week 8, the weight taken at the prior visit may be used to calculate dose (e.g. weight at Week 8 used for Week 9 dosing)
- disease assessment (see [Appendix D. Table 3](#)) at the end of Weeks 16 and 24, followed by every 12 weeks (Weeks 36, etc.) or at the point that clinical progression is observed or suspected.
  - For CTCL and PTCL subjects, central submission of radiographic disease assessments is required.
  - CTCL subjects only: mSWAT, CAILS (if applicable) and photographs at time of disease assessments
  - Peripheral blood and blood smear for central pathology review for SS subjects only. Refer to the Laboratory Manual and to [Appendix D. Table 3](#) for additional details.
- Week 16 pre-infusion: fresh tumor sample from an identified target lesion for CTCL subjects only
- resting 12-lead ECG Day 1 of Weeks 16 and 24
- QOL by FACT-G (all subjects) and SKINDEX29 (CTCL only): post-dose on Week 16 and 24, and then every 12 weeks thereafter
- urine or serum pregnancy test for women of childbearing potential Day 1 of Week 12 and every 4 weeks thereafter
- serum chemistries Day 1 of Week 12 and every 4 weeks thereafter
- hematology Day 1 of every week (results must be available prior to start of infusion). Further hematologic monitoring should be instituted at the discretion of the treating investigator.

- serum for PK (see [Table 7-2](#)):
  - Day 1 of Week 9 and every week through Week 16 inclusive: trough level (pre-infusion)
- biomarkers ( $\pm$  15 minutes; see Study Manual for details of sample preparation and shipping):
  - Day 1 of Week 9 (pre-infusion): serum for cytokine/chemokine panel
  - Day 1 of Week 16 (pre-infusion): whole blood TCR V $\beta$  sequencing
  - Day 1 of Week 16 only (pre-infusion): anti-tumor antibodies
  - Day 1 of Week 9 (pre-infusion): whole blood for receptor occupancy
- TSH on Day 1 of Week 12 and every 12 weeks thereafter (only for subjects in the nivolumab combination cohort)
- serum for ADA analysis pre-infusion on Day 1 of Week 12 and every 4 weeks
- AEs
- concomitant medications

### 7.10.2 Phase 1b Part 4

The following assessments are applicable for patients under Part 4. Refer to [Appendix D. Table 2](#). The procedures listed below will be performed at the indicated time relative to the infusion of TTI-621. All assessments can be performed up to 24 hours pre-infusion, with the exception of PK and biomarkers.

- Day 1 of Week 12, and every 4 weeks thereafter:
  - coagulation, symptom driven from week 16 onward
  - resting 12-lead ECG
  - urine or serum pregnancy test for women of childbearing potential
  - serum chemistries
- body weight measured every other week (Week 10, 12, etc.). After Week 8, the weight taken at the prior visit may be used to calculate dose (e.g. weight at Week 8 used for Week 9 dosing)
- vital signs pre-infusion, performed per the institutional standard of care weekly
- disease assessment (see [Appendix D. Table 3](#)) at the end of Weeks 16 and 24, followed by every 12 weeks (Weeks 36, etc.) or at the point that clinical progression is observed or suspected.

- central submission of radiographic disease assessments is not required for central review in real time but retrospective submissions might be requested by sponsor.
- mSWAT, CAILS (if applicable) and photographs
- QOL by FACT-G and SKINDEX29
- hematology Day 1 of every week (results must be available prior to start of infusion). Further hematologic monitoring should be instituted at the discretion of the treating investigator.
- symptom driven physical examination/ECOG score Day 1 of every week
- AEs
- concomitant medications
- serum for PK (see [Table 7-2](#)):
  - Day 1 of Week 9 and every week through Week 16 inclusive: trough level (pre-infusion)
- biomarkers ( $\pm$  15 minutes; see Study Manual for details of sample preparation and shipping):
  - Week 16 pre-infusion: fresh tumor sample if feasible from the same lesion as screening or from a nearby lesion for CTCL subjects only
  - whole blood for receptor occupancy pre-infusion on Day 1 of Week 12 and 16.
- serum for ADA analysis pre-infusion on Day 1 of Week 12 and every 4 weeks

## 7.11 End-of-Treatment Visit

Within 1 week following the final dose of TTI-621 (or at the time of premature discontinuation of treatment), the following procedures will be performed:

- physical examination and ECOG score
- body weight
- vital signs
- disease assessment (if not performed within the last 8 weeks)
- QOL by FACT-G (all subjects) and SKINDEX29 (CTCL only)
- resting 12-lead ECG
- serum for PK
- serum chemistries
- hematology

- coagulation panel
- TSH (only for subjects in the nivolumab combination cohort)
- urinalysis
- serum for ADA analysis
- biomarkers (see Study Manual for details of sample preparation and shipping):
  - serum for cytokine/chemokine panel (not required for Part 4)
  - whole blood for innate and adaptive response assay (not required for Part 4)
- AEs
- concomitant medications
- peripheral blood and blood smear for central pathology for SS patients (Part 3 only). Refer to the Laboratory Manual and to [Appendix D. Table 3](#) for additional information.

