### 7.1 Screening Period

Informed consent may be obtained within 30 days prior to Day 1, after which it is recommended that the subject be re-consented. The following procedures will be performed after written informed consent has been obtained and within 14 days prior to the planned start of treatment unless otherwise noted:

- physical examination including review of systems (breast/chest, extremities, head/ears/eyes/nose/throat, lymph nodes, musculoskeletal, pulmonary and skin), and height
- body weight

- ECOG performance status (see [Appendix B](#))
- vital signs including heart rate, respiratory rate, and body temperature
- baseline disease assessment as indicated for the specific primary malignancy (see [Section 7.14.1](#) and [Appendix D. Table 3](#)) within 28 days prior to the planned start of treatment. CTCL: mSWAT, CAILS (local disease only) and central photographs.
  - Leukemia and lymphoma with marrow involvement: bone marrow aspirate for routine morphology, flow cytometry, CD47 expression and receptor occupancy (not required for Part 4)
  - CTCL: photographs of tumor lesions will be captured at the clinical site(s) using standardized photographic equipment, methodologies and services provided by Canfield Scientific, Inc. (Parsippany, New Jersey). Further detail for study photography will be provided in the supplied Canfield User Manual
- CTCL and PTCL (Part 3 only): Radiographic disease assessments for CTCL and PTCL will be submitted for central review (central results are not required for enrollment). Please refer to the Imaging Manual. Part 4 will not require submission of scans for central review in real time but retrospective submissions might be requested by sponsor.
- CTCL and PTCL (Part 3 only): Tumor tissue will be submitted for central review for subjects with CTCL (not including SS) and PTCL to confirm the diagnosis (central disease confirmation not required for enrollment). For subjects with SS, peripheral blood is acceptable. Archival tissue may be provided. Refer to the Laboratory Manual for additional details.
- resting 12-lead ECG
- hepatitis B (HBsAg and HBcAb) and C (HCV Ab) panel
- serum pregnancy test for women of childbearing potential

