### *Response-Evaluable Set*

The Response-Evaluable Set will serve as the primary population for the analysis of overall response. The Response-Evaluable Set is a subset of the Full Analysis Set, with subjects excluded if they have no post-baseline assessment of overall response.

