#### 8.4.6 Efficacy Analyses

Efficacy analyses will be conducted using the Full Analysis Set and, where appropriate, the Per-protocol Set; in addition, the overall response rate will also be presented for the Response-Evaluable Set.

The overall response rate will be estimated for each cohort using disease-specific response criteria (see [Section 7.14.1](#)). The duration of response (DOR) will be calculated for a subject who achieves a response, and is defined as the number of weeks from the start date of the response (and subsequently confirmed) to the first date recurrent or progressive disease is documented. If a subject dies, irrespective of cause, without documentation of recurrent or progressive disease beforehand, then the date of death will be used to denote the response end date.

Progression-free survival (PFS) is defined as the number of weeks from the date of the first dose of study drug to the earliest of documented recurrent or progressive disease or death due to any cause without prior progression. Leukemia-free survival (LFS) will be calculated in the same manner, as appropriate.

DOR and PFS will be summarized descriptively using the Kaplan-Meier method with 95% CI calculated using Greenwood's formula. Median follow-up for each endpoint will be estimated according to the Kaplan-Meier estimate of potential follow-up. The PFS rate at selected landmarks (e.g., 6 months) and corresponding 95% CIs will be estimated using the Kaplan-Meier method. Greenwood's formula will be used to calculate the standard errors of the Kaplan-Meier estimate and upper and lower limits of the 95% CI.

For DOR and PFS, subjects who meet one or more of the following conditions will be right-censored as follows:

- subjects with no baseline or postbaseline disease assessments unless death occurred prior to the first planned assessment (in which case the death will be considered a PFS event)
- subjects who initiate subsequent anticancer therapy in the absence of documented progression
- subjects who die or have disease progression after missing 2 or more consecutively scheduled disease assessment visits
- subjects who are last known to be alive and progression-free on or before the data cut-off date

For such subjects, the progression or censoring date will be determined based on described conventions (Food and Drug Administration, 2007), as outlined in the SAP.

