## Footnotes

- a Screening laboratories may be used as pre-dose baseline if within 3 days of Day 1
- b Review of systems and physical exam: breast/chest, extremities, head/ears/eyes/nose/throat, lymph nodes, musculoskeletal, pulmonary, skin, height. Symptom driven on all treatment weeks and SFU. Full exam at screening and EOT.
- c Including heart rate, respiratory rate, body temperature.
- d See [Appendix D. Table 3](#) and [Section 7.14.1](#) for further details, including disease assessment scales. For CTCL and PTCL subjects, central submission of radiographic disease assessment is required. Also for CTCL subjects only: mSWAT, CAILS (if applicable) and photographs. All response assessments should be performed at the end of the indicated weeks and the time points have a window of  $\pm 1$  week.
- e If treatment-emergent abnormalities are present at end of treatment, repeat pertinent labs or studies
- f Subjects who are seropositive at end of safety follow-up should be monitored at least quarterly for 1 year post study to assess persistence of antibodies.
- g If not already included in the regular scheduled visit assessment, these are to be performed for dose-intensified subjects in addition to the regularly scheduled visit assessments. Dose intensification to occur from Week 3 to Week 8. After Week 9, additional dose intensification is not permitted.
- h For subjects with SS, peripheral blood is acceptable, if a biopsy is not possible. For all other subjects fresh tumor biopsy required if feasible. Archival tissue at screening acceptable, if biopsy not feasible.
- i If not done in prior 8 weeks
- j Within 1 week following the final dose of TTI-621 (or at the time of premature discontinuation of treatment)
- k Within 28 days of planned start of treatment
- l Blood for peripheral receptor occupancy to be drawn pre-infusion and 1 hr post-infusion (EOI) at each dose-intensification and at Week 8
- m 12-lead ECG within approximately 30 minutes of completion of infusion (i.e., 60–90 minutes after Time 0)
- n For subjects with marrow based disease only, at time of disease assessments
- o Or at the time of observed or suspected clinical progression
- p  $\pm 1$  week to align with response assessments

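### A baseline assessment can waive the end-of-treatment disease assessment, so Part 2 and 3 subjects who stop before Week 8 can leave with no post-baseline assessment, which biases PFS upward and exposes a protocol–SAP conflict on response

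*Protocol*

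**What the plan says.** **Waiver.** Protocol Section 7.11 includes "disease assessment (if not performed within the last 8 weeks" in the end-of-treatment visit. Appendix D Table 1 footnote i and Table 2 footnote g say the same: "If not done in prior 8 weeks". Appendix D Table 3 marks an end-of-treatment assessment for every disease and attaches no waiver.

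**Timing.** Baseline disease assessment is due "within 28 days prior to the planned start of treatment" (7.1). The first on-treatment one is the Week 8 "disease assessment at the end of the week" (7.9), with a window of one week either side (Section 7). The end-of-treatment visit takes place "Within 1 week following the final dose of TTI-621 (or at the time of premature discontinuation of treatment" (7.11). The trigger "or at the point that clinical progression is observed or suspected" appears in 7.10, which covers Weeks 9 and higher; the matching footnotes in Appendix D Tables 1 and 2 sit in the Week 9+ column.

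**PFS.** Protocol 8.4.6 right-censors "subjects with no baseline or postbaseline disease assessments unless death occurred prior to the first planned assessment"; such a death counts as an event. SAP 3.7.1 and 3.7.2 take the progression date from the first assessment scored as progressive disease.

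**Response.** Protocol 8.2 makes the Response-Evaluable Set primary for overall response, with "subjects excluded if they have no post-baseline assessment of overall response". Protocol 8.4.7 counts the Simon stages in response-evaluable subjects. SAP Section 2 makes the Full Analysis Set primary. It limits the Response-Evaluable Set to Part 3 and keeps in it subjects who leave unassessed because of early progression or safety. SAP 3.7.1 counts missing responses as non-response.

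**The concern.** An end-of-treatment assessment should record disease status in anyone who leaves between scheduled assessments. Here it can be skipped in exactly the subjects who have nothing after baseline, because the baseline assessment itself may be less than 8 weeks old. Those who stop in the first weeks are likely to include many treatment failures. If their status is never recorded, the failures become censored times in PFS and, under the protocol's definition, disappear from the response denominator. The Part 3 decision on going to Stage 2 and on rejecting the drug uses that denominator.

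**Working it through.** **1. How long a baseline assessment satisfies the waiver.** Inputs: 8 weeks = 56 days (7.11); baseline *s* days before Day 1, with *s* from 0 to 28 (7.1). Study Day *d* is *d* − 1 days after Day 1, so the interval is *s* + *d* − 1. The assessment is waived while *s* + *d* − 1 ≤ 56, that is, through Day 57 − *s*.

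| Baseline, days before Day 1 | Visit waived through | Final-dose weeks covered if the visit is 7 days after the dose |
|---|---|---|
| 28 | Day 29 | 1–4 |
| 21 | Day 36 | 1–5 |
| 14 | Day 43 | 1–6 |
| 7 | Day 50 | 1–7 |
| 0 | Day 57 | 1–8 |

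The waiver therefore reaches from 29/56 = 52% to all of Days 1–56, depending on the baseline date.

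**2. Whether anything else requires an assessment before Week 8.** The trigger for suspected progression is written only for Weeks 9 and higher. The title of Appendix D Table 1 allows additional assessments when clinically indicated, which permits one without requiring it. Appendix D Table 3 shows the end-of-treatment assessment with no exception, so the protocol gives two answers.

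**3. PFS.** An early stopper with no post-baseline assessment is censored under protocol 8.4.6 unless death comes before the first planned assessment. The SAP cannot record progression for that subject without an assessment scored as progressive disease. The SAP censoring table has no row for a subject with no post-baseline assessment, so the censoring date is not defined. Censoring subjects who have in fact progressed makes the Kaplan-Meier curve too high. The size depends on how many stop unassessed, how many of those had progressed, and the censoring date; the documents give none of these. As an upper end only: if a fraction *q* of subjects progressed unassessed and all were censored at Day 1, the estimate is S/(1 − *q*). For an assumed true 26-week PFS of 0.30 this gives:
- *q* = 10%: 0.30/0.90 = 0.333
- *q* = 20%: 0.30/0.80 = 0.375
- *q* = 30%: 0.30/0.70 = 0.429

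**4. Simon rule, the plan's own figures.** Inputs from protocol 8.3: n1 = 18, r1 = 2, N = 35, r = 6, p0 = 0.10, p1 = 0.30.
- PET = P(X1 ≤ 2 | 18, 0.10) = 0.734
- Average N = 18 + (1 − 0.7338) × 17 = 22.53
- Type I error = Σ over x1 ≥ 3 of P(X1 = x1) × P(X2 ≥ 7 − x1 | 17, 0.10) = 0.047
- Beta, from the same sum at 0.30: 1 − 0.9016 = 0.098

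All four match the stated values.

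**5. Simon rule under the protocol's Response-Evaluable Set.** Suppose a fraction *d* of treated subjects is excluded as unassessed, all are non-responders, and enrollment continues until 18 and then 35 are evaluable. The evaluable response rate is then 0.10/(1 − *d*) when the rate in all treated subjects is 0.10. The documents give no value for *d*; the values below are assumed.

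| *d* | Evaluable rate | PET | Type I error |
|---|---|---|---|
| 0 | 0.100 | 0.734 | 0.047 |
| 10% | 0.111 | 0.677 | 0.075 |
| 20% | 0.125 | 0.605 | 0.121 |
| 30% | 0.143 | 0.515 | 0.199 |

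**6. The same rule under the SAP's set.** Subjects who leave for early progression or safety stay in as non-responders and cause no inflation. Only subjects leaving unassessed for other reasons, such as withdrawal of consent, are still excluded.

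**The case against.** The strongest reply is that the SAP has already dealt with response. It keeps the likely failures in the Response-Evaluable Set, makes the Full Analysis Set primary and counts missing as non-response. That stands for the SAP's own response rates. It does not settle the Simon rule: the protocol defines that rule on its stricter set, and the SAP restates the rule without naming a denominator of its own.

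On PFS, four points can be made.
- The waiver does not forbid an assessment. This is true, but it leaves the decision to the site.
- Protocol 6.9 ties withdrawal for progression to the disease assessment section, so such a subject would often have an assessment behind the decision. This reduces the problem, but no assessment is required before Week 9 and subjects also stop for other reasons.
- Long-term follow-up (7.13) collects a progression date not documented on study, and early deaths are events. Both limit the loss. However, the SAP's progression definition does not name the follow-up date as a source, and progression after new anticancer therapy is censored.
- PFS is not a listed endpoint in Part 4. This stands; the PFS consequence concerns Parts 2 and 3.

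A reader might also infer that baseline always satisfies the waiver for any stop before Week 8. It does not: a baseline assessment done 28 days before Day 1 no longer covers a visit after Day 29, and the Week 8 assessment may itself be done up to a week early.

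**Conclusion.** The gap is real and has a narrow cause: the waiver is not limited to post-baseline assessments, and Appendix D Table 3 contradicts it. Subjects in Parts 2 and 3 who stop before Week 8 can therefore leave with no required post-baseline assessment. PFS is then biased upward by an unknown amount. The values in step 3 of the working should not be read as an estimate: they assume that every unassessed subject had progressed, that none died, that no follow-up date was used, and that all were censored at Day 1.

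A reader might infer that the Simon type I error is inflated in the trial as analysed. The documents support that only under the protocol's Response-Evaluable Set, with the assumed 10–30% exclusion and every excluded subject a non-responder; the result is then about 0.075 to 0.20 instead of 0.047. Under the SAP's definition, subjects who leave for progression or safety add nothing to it. Response rate and PFS are secondary endpoints and the primary endpoint, adverse events, is untouched. The correction matters mainly for PFS and for the denominator of the Part 3 decision.

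**What to change.** 1. In Section 7.11, Appendix D Table 1 footnote i and Table 2 footnote g, waive the end-of-treatment disease assessment only if a post-baseline disease assessment was done in the last 8 weeks. Put the same condition on the end-of-treatment column of Appendix D Table 3.
2. Use the SAP Section 2 definition of the Response-Evaluable Set for the Simon rule in both documents, so that subjects who leave for early progression or safety stay in as non-responders.
3. In SAP 3.7.2, state the censoring date for a subject with no post-baseline assessment. Add a PFS sensitivity analysis that counts discontinuation for progression without a post-baseline assessment as an event at the discontinuation date. This should stay a sensitivity analysis: making the investigator's stated reason an event in the main analysis of an open-label study would replace one bias with an unverified judgement.

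The cost is small. A few early leavers have an assessment that is already on the schedule, and reported PFS may be slightly lower. The sensitivity analysis needs no new data, because reasons for discontinuation are already summarized (SAP 3.1). For subjects who have already left, only items 2 and 3 can help.
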